9. SAFETY ASSESSMENTS

See Section 1 for the timing of all safety assessments.

Tests and evaluations affecting primary endpoints and/or analyses may need to be repeated if the original results are lost or damaged. In these cases, participants will be asked to return to the clinic to have the evaluations repeated.

9.1. Clinical Assessments

The following clinical assessments will be performed to evaluate the safety profile of BIIB105:

- AE and SAE recording.
- Physical examinations.
- Neurological examinations (to be assessed by a trained specialist): Cranial nerves, motor, reflexes, cerebellar function, and mental status (MMSE in Part 1). A detailed list will be provided in the Study Reference Manual.
- Vital sign measurements: Temperature, heart rate, systolic and diastolic blood pressure, and respiratory rate will be measured after the participant has rested for at least 5 minutes.
- Weight and height measurements.
- 12-Lead ECGs: ECGs are to be done in triplicate in the supine position (or semi-recumbent position, if supine is not possible).
- C-SSRS:
 - In Part 1, the "Since Last Visit" version of C-SSRS will be used from Day 8 onward.
 - In Part 2, participants from Cohorts D1 and D2 will use "Since Last Visit" version of C-SSRS on Day 1 onward. Participants from Cohorts A, B, C1, and C2 will use the "Since Last Visit" version of the C-SSRS from Day 15 onward.
- Concomitant therapy and procedure recording.

9.2. Laboratory Assessments

Samples will be analyzed using Good Laboratory Practice-validated assays.

The following laboratory assessments will be performed to evaluate the safety profile of BIIB105:

- Hematology: Complete blood count with differential
- Coagulation: INR, PT, and APTT
- Blood chemistry: Total protein, albumin, HbA1c, lipid panel, creatinine, blood urea nitrogen, uric acid, bilirubin (total and direct), alkaline phosphatase, alanine aminotransferase, aspartate aminotransferase, gamma-glutamyl transferase, glucose, calcium, phosphorus, bicarbonate, chloride, sodium, and potassium
- Urinalysis: Dipstick for blood, protein, and glucose (microscopic examination, if abnormal)
- Urine and/or serum pregnancy tests
- CSF analysis: Red blood cell count, white blood cell count, protein, and glucose

9.3. Product-Specific Safety Assessments

Anti-BIIB105 antibody assessments will be conducted when indicated.

10. PHARMACOKINETIC ASSESSMENTS

BIIB105 concentrations in the serum and CSF will be determined using validated assays.

Samples for analysis of BIIB105 concentrations in serum and CSF will be collected from each participant at timepoints specified in Table 1 and Table 2.

See Section 1 for the timing of all assessments.

The following PK parameters will be assessed, when feasible, to assess the PK of BIIB105:

- AUC_{inf}
- AUC_{last}
- C_{max}
- T_{max}
- t_{1/2}

Additional PK parameters may be calculated at the discretion of the Pharmacokineticist.

11. PHARMACODYNAMIC AND EFFICACY ASSESSMENTS

See Section 1 for the timing of all assessments.

11.1. Pharmacodynamic Assessments

, plasma, will be collected to assess the modulation of potential PD biomarkers that may be related to BIIB105 activity or ALS disease progression. The assessments may include, but are not limited to, . The biomarkers to be analyzed may include, but are not limited to, ATXN2, NfL,

11.2. Assessments of Clinical Function and Survival

The following assessments will be performed to evaluate the effects of BIIB105 on clinical function and survival:

- SVC
- ALSFRS-R (standard)
- •
- •
- •
- HHD
- •
- •
- •
- Ventilation diary
- Collection of vital status before and after study withdrawal or completion

11.2.1. Slow Vital Capacity

Vital capacity will be measured by means of an SVC test, collected by certified assessors according to a standardized protocol established by the Northeast ALS Consortium.

11.2.2. ALS Functional Rating Scale-Revised (standard)

The ALSFRS-R has been demonstrated to predict survival. The ALSFRS-R measures 4 functional domains, including respiratory, bulbar function, gross motor skills, and fine motor skills. There are 12 questions, each scored from 0 to 4, for a total possible score of 48, with higher scores representing better function [Cedarbaum 1999]. At each study site, the same qualified and trained study site staff member will consistently perform the ALSFRS-R for a participant. A qualified and trained backup ALSFRS-R rater will be identified in case the primary rater is unavailable. In Part 1, this study site staff member will remain blinded to participants' treatment assignments and to the results of other assessments. In Part 2, this study site staff member will remain blinded to participants' treatment assignments and to the results of other assessments during the blinded loading dose period for participants in Cohorts D1 and D2.

11.2.6. Handheld Dynamometry

Muscle strength is an important determinant of both function and ultimate survival in ALS. Quantitative muscle strength will be evaluated using HHD, which tests isometric strength of multiple muscles using standard participant positioning [Shefner 2016]. Approximately 8 muscle groups will be examined (per each side) in both upper and lower extremities.

11.2.10. Participant Ventilation Diary

Participants will be given diaries to record use of ventilation. This diary will be reviewed with study site staff at each visit. Refer to the Study Reference Guide for details.

11.2.11. Collection of Vital Status Before and After Study Withdrawal or Completion

Participants' vital status will be collected throughout the study. For participants who provide optional consent for data collection after study withdrawal or completion, follow-up on vital status and date of death (if deceased) will be performed.

11.3. Pharmacogenetic and Genetic Assessments

Genetic polymorphism impacting genes encoding drug targets or the downstream pathways, as well as proteins that impact drug absorption, distribution, metabolism, and elimination, may affect the safety and efficacy of the study treatment.

A DNA sample will be collected for genomic analysis. This is a one-time blood collection required at Screening for all participants, as outlined in Table 1 and Table 2. For all cohorts, this collection is governed by the main ICF for the study.

Approximately 10% of patients diagnosed with ALS are known to be caused by genetic mutations; to date, at least 20 genes have been identified as causative of, or highly associated with ALS, including the *ATXN2* intermediate polyCAG repeat mutation. The DNA sample will be used to determine the presence or absence of an *ATXN2* intermediate polyCAG repeat mutation. The DNA sample may also be analyzed for genetic variation in the *ATXN2* gene to determine the spectrum of likely pathogenic mutations in the gene and to assess if *ATXN2* polymorphisms affect response to treatment. In addition, these samples may be analyzed for genetic variation in other genes of known and probable relevance for the pathogenesis of ALS and neurodegeneration, including but not limited to *TAR DNA binding protein*, *FUS*, *chromosome 9 open reading frame 72*, *optineurin*, *valosin-containing protein*, *ubiquilin 2*, *profilin 1*, and *SOD1*.

In the event of an unusual response or observation of unexplained AEs, DNA samples may be used to determine if there are any pharmacogenetic associations with drug response.

In the future, as the understanding of ALS and BIIB105 increases, additional genetic analyses may be warranted to refine the knowledge of the molecular basis of the disease and the drug response and to advance the development of novel therapeutics. This sample will only be used in genetic analyses to understand ALS, neurodegeneration, and the response to BIIB105.

The DNA samples will be coded with the participant's identification number and may be stored for 15 years or a duration dictated by local, national, or regional laws or regulations. No genotyping or genetic data will be provided to the participant. Participants may withdraw consent and request to have their sample destroyed at any time and no further genetic data will be generated; any data already generated will not be destroyed.

In addition, where allowed by local, regional, and national regulatory authorities and ethics committees, participants will be offered the option for that may be used to understand the biology of ALS and other diseases and traits of interest to the Sponsor and/or to develop diagnostic and

analytical tests. Participants who opt for samples to be retained for future unspecified use will be required to sign a separate ICF.

12. SAFETY DEFINITIONS, RECORDING, REPORTING, AND RESPONSIBILITIES

Throughout the course of the study, every effort must be made to remain alert to possible AEs. If an AE occurs, the first concern should be for the safety of the participant. If necessary, appropriate medical intervention should be provided.

At the signing of the ICF, each participant and/or his/her legally authorized representative and/or main informant/caregiver must be given the names and telephone numbers of site staff for reporting AEs and medical emergencies. Throughout the protocol, the Sponsor is named, but reporting may be done through a CRO.

12.1. **Definitions**

12.1.1. Adverse Event

An AE is any untoward medical occurrence in a patient or clinical investigation participant administered a pharmaceutical product and that does not necessarily have a causal relationship with this treatment. An AE can therefore be any unfavorable and unintended sign (including an abnormal laboratory finding), symptom, or disease temporally associated with the use of a medicinal (investigational) product, whether or not related to the medicinal (investigational) product.

Determination of whether an abnormal assessment (e.g., laboratory value, vital sign, and ECG) result meets the definition of an AE will be made by the Investigator. Abnormal results are not considered AEs unless one or more of the following criteria are met:

- The result meets the criteria for an SAE.
- The result requires the participant to receive specific corrective therapy.
- The result is considered by the Investigator to be clinically significant.

12.1.2. Serious Adverse Event

An SAE is any untoward medical occurrence that at any dose:

- Results in death.
- In the view of the Investigator, places the participant at immediate risk of death (a life-threatening event); however, this does not include an event that, had it occurred in a more severe form, might have caused death.
- Requires inpatient hospitalization or prolongation of existing hospitalization.
- Results in persistent or significant disability/incapacity.

- Results in a congenital anomaly/birth defect.
- Is a medically important event.

A medically important event is an AE that, in the opinion of the Investigator, may jeopardize the participant or may require intervention to prevent one of the other outcomes listed in the definition above. (Examples of such medical events include allergic bronchospasm requiring intensive treatment in an emergency room or convulsions occurring at home that do not require an inpatient hospitalization.)

12.1.3. Prescheduled or Elective Procedures or Routinely Scheduled Treatments

A prescheduled or elective procedure or a routinely scheduled treatment will not be considered an SAE, even if the participant is hospitalized. The study site must document all of the following:

- The prescheduled or elective procedure or routinely scheduled treatment was scheduled (or was on a waiting list to be scheduled) prior to obtaining the participant's consent to participate in the study.
- The condition requiring the prescheduled or elective procedure or routinely scheduled treatment was present before and did not worsen or progress in the opinion of the Investigator between the participant's consent to participate in the study and the time of the procedure or treatment.
- The prescheduled or elective procedure or routinely scheduled treatment is the sole reason for the intervention or hospital admission.
- If a participant is hospitalized due to local requirements for administration of the study treatment, the hospitalization should not be considered an SAE unless one of the requirements in Section 12.1.2 is met.

12.2. Safety Classifications

12.2.1. Investigator Assessment of Events

All events must be assessed to determine the following:

- If the event meets the criteria for an SAE as defined in Section 12.1.2.
- The relationship of the event to study treatment or LP as defined in Section 12.2.2.
- The severity of the event as defined in Section 12.2.3.

12.2.2. Relationship of Events to Study Treatment or Lumbar Puncture

The following definitions should be considered when evaluating the relationship of AEs and SAEs to the study treatment or LP.

Relationship of Event to Study Treatment				
Not related	An AE will be considered "not related" to the use of the investigational product if there is not a reasonable possibility that the event has been caused by the product under investigation. Factors pointing toward this assessment include but are not limited to the lack of reasonable temporal relationship between administration of the investigational product and the AE, the presence of a biologically implausible relationship between the product and the AE, or the presence of a more likely alternative explanation for the AE.			
Related	An AE will be considered "related" to the use of the investigational product if there is a reasonable possibility that the event may have been caused by the product under investigation. Factors that point toward this assessment include but are not limited to a positive rechallenge, a reasonable temporal sequence between administration of the investigational product and the AE, a known response pattern of the suspected product, improvement following discontinuation or dose reduction, a biologically plausible relationship between the product and the AE, or a lack of an alternative explanation for the AE.			

Relationship of Event to Lumbar Puncture			
Not related	An AE will be considered "not related" to the LP procedure if there is not a reasonable possibility that the event has been caused by the LP procedure. Factors pointing toward this assessment include but are not limited to the lack of reasonable temporal relationship between the LP procedure and the AE, the presence of a biologically implausible relationship between the LP procedure and the AE, or the presence of a more likely alternative explanation for the AE.		
Related	An AE will be considered "related" to the LP procedure if there is a reasonable possibility that the event may have been caused by the LP procedure. Factors that point toward this assessment include but are not limited to a reasonable temporal sequence between the LP procedure and the AE, a known response pattern of the LP procedure (e.g., bleeding from the puncture site), a biologically plausible relationship between the LP procedure and the AE, or a lack of an alternative explanation for the AE.		

12.2.3. Severity of Events

The severity of AEs and SAEs will be graded using the National Cancer Institute CTCAE (version 4). Any AE not listed in the CTCAE will be graded as follows:

Severity of Event				
Grade	Definition			
1	Mild AE (asymptomatic or mild symptoms; clinical or diagnostic observations only; intervention not indicated)			
2	Moderate AE (minimal, local, or noninvasive intervention indicated; limiting age-appropriate instrumental activities of daily living)			
3	Severe or medically significant AE (not immediately life-threatening; hospitalization or prolongation of hospitalization indicated; disabling; limiting self-care activities of daily living)			
4	Life-threatening AE (urgent intervention indicated)			
5	Death related to AE			

12.2.4. Expectedness of Events

Expectedness of all AEs will be determined by the Sponsor according to the Investigator's Brochure for BIIB105.

12.3. Monitoring and Recording Events

12.3.1. Adverse Events

Any AE experienced by the participant between the time of first dose of study treatment and the Final/ET Visit is to be recorded on the CRF, regardless of the severity of the event or its relationship to study treatment. At each study visit, the Investigator will assess the participant for AEs and will record any new AEs or updates to previously reported AEs on the CRF.

AEs that are ongoing when the participant completes or discontinues the study will be followed up by the Investigator until the event has resolved, stabilized, or returned to baseline status. AE outcome will be recorded on the CRF, as applicable.

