3.3. Benefit-Risk Assessment

The potential benefit of BIIB105 in ALS has not been established. This study has been designed with appropriate dose escalation, safety monitoring, and stopping rules to minimize risks to participants. The results of this study may offer key insights into the development of a disease-modifying therapy for ALS.

This is a first in human study, thus the risk in humans is unknown. Emerging clinical data can be found in the Investigator's Brochure.

Nonclinical work with *Atxn2* homozygous knockout mice suggests that ATXN2 reduction could be associated with risks of metabolic complications (adult-onset obesity and insulin resistance) and subtle neurological deficits [Huynh 2009; Kiehl 2006; Lastres-Becker 2008]. Human data from the Genome-Wide Association Studies database suggest that variation in *ATXN2* could be associated with changes in blood pressure and cardiometabolic phenotypes [Auburger 2014]. From the nonclinical safety studies in NHPs, the adverse effect level was considered to be mg based on severe but reversible and monitorable clinical signs: 1 of 3 animals exhibited increased muscle tone, whole body spasms, and tremors that required administration of diazepam. The animal fully recovered by hours. No adverse metabolic effects were seen in toxicology studies. Participants will be monitored in the clinical setting with neurological and physical examinations and careful monitoring of blood chemistries, among other safety assessments.

Although LP is generally considered a safe procedure, certain complications can occur in a subset of patients. These may include, but are not limited to, back pain, headache, nausea, infection, bleeding, radicular pain and numbness, and bruising or injury at the injection site. These potential risks can be mitigated by using atraumatic needles, avoiding contraindicated medications, and testing coagulation and platelet counts prior to the procedure. Importantly, life-threatening cerebral herniation is a possible complication of a lumbar puncture procedure.

Reproductive toxicity studies were conducted in mice and rabbits using SC administration of BIIB105 once every other day. In a definitive combined fertility and embryo-fetal development

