7.5. Precautions

Depending on institutional guidelines, anesthesia or sedation may be used for the LP procedure. On dosing days in Part 1, (except Dose 1), participants will remain at the study site for at least 6 hours postdose for safety monitoring. In Part 2, participants who receive the 60 mg dose will remain at the study site for at least one hour postdose, and participants who receive the 120 mg dose will remain at the study site for at least 2 hours postdose for safety monitoring. Participants can be discharged at the discretion of the Investigator and in compliance with the institutional requirements, once the participant has adequately recovered from the dosing procedure. Participants will receive a safety follow-up TC approximately 24 hours after the procedure. During the Follow-up Period, participants will remain under observation in the clinic for approximately 1 hour after the LP procedure and will receive a safety follow-up TC approximately 24 hours after the procedure. Refer to and follow the DHA.

Any antiplatelet or anticoagulant medication that cannot be safely interrupted for an LP procedure, if necessary, according to local or institutional guidelines and/or Investigator determination is prohibited for the duration of the study.

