12.3.2. Serious Adverse Events

Any SAE experienced by the participant between the time of the signing of the ICF and the Final/ET Visit is to be recorded on an SAE form, regardless of the severity of the event or its relationship to study treatment and must be reported to the Sponsor within 24 hours as described in Section 12.3.3. Follow-up information regarding an SAE also must be reported within 24 hours.

A Phase 1/2 MAD Study and Long-Term OLE in Adults With ALS With or Without ATXN2 PolyCAG Expansion

Participants will be followed up for all SAEs until the final study visit. Thereafter, the event should be reported to the Sponsor only if the Investigator considers the SAE to be related to study treatment.

Any SAE that is ongoing when the participant completes or discontinues the study will be followed up by the Investigator until the event has resolved, stabilized, or returned to baseline status.

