5.7.1. Adverse Events

All AEs will be classified using MedDRA version 26.1 or later if available. Only treatment emergent AEs (TEAEs) will be summarized, where treatment emergence will be relative to the first dose of study drug. A treatment emergent AE/SAE is defined as any AE/SAE with an onset date that is on or after the first dose of study drug or any pre-existing condition that has worsened in severity after the first dose of study drug. Whenever possible, date/time will be used to determine whether an event is treatment emergent. If an event date (start or end) is incomplete, a TEAE will be determined assuming most conservative way as follows:

- If onset day is missing and the month and year are the same as or after the treatment start date, then that event is considered treatment emergent.
- If both onset month and day are missing and the year is the same as or after the treatment start date, then that event is considered treatment emergent.
- If both onset date and end date are completely missing, an event will be considered as a TEAE.
- If onset date is completely missing and end date is not missing which is after the first dose of study drug, an event will be considered as a TEAE.

The incidence of TEAEs will be summarized by dose level (or cohort) and overall BIIB105 as follows:

- Overall summary of TEAE
- TEAEs by primary SOC and MedDRA preferred term
- TEAEs by MedDRA preferred term
- SAEs by primary SOC and MedDRA preferred term
- SAEs by MedDRA preferred term
- Related SAEs by primary SOC and MedDRA preferred term
- TEAEs by CTCAE grading, primary SOC and MedDRA preferred term
- TEAEs with severity greater than or equal to 3 by primary SOC and MedDRA preferred term
- Related TEAEs by primary SOC and MedDRA preferred term
- TEAEs that led to discontinuation of study treatment by primary SOC and MedDRA preferred term
- TEAEs that led to study drug interruption by primary SOC and MedDRA preferred term

CONFIDENTIAL

The information contained herein may not be used, disclosed, or published without the written consent of Biogen MA Inc.

- TEAEs that led to withdrawal from study by primary SOC and MedDRA preferred term
- TEAEs related to the lumbar puncture by primary SOC and MedDRA preferred term
- TEAEs that led to death by primary SOC and MedDRA preferred term
- TEAEs within 24 hours of dosing by primary SOC and MedDRA preferred term

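### AE and SAE recording is written to stop at the Final/ET Visit, a day before the planned safety call about that visit's lumbar puncture, and the rule for later SAEs leaves out LP-related events

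*Protocol*

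**What the plan says.** - **AE window.** Protocol Section 12.3.1: an AE experienced "between the time of first dose of study treatment and the Final/ET Visit is to be recorded on the CRF".
- **SAE window.** Section 12.3.2 covers "Any SAE experienced by the participant between the time of the signing of the ICF and the Final/ET Visit". For anything later, "the event should be reported to the Sponsor only if the Investigator considers the SAE to be related to study treatment".
- **Causality.** Section 12.2.1 requires each event to be assessed for "The relationship of the event to study treatment or LP as defined in Section 12.2.2". Section 12.2.2 then gives separate related/not-related definitions for study treatment and for LP.
- **LP and call.** Tables 1 to 3 mark CSF sampling at the Final/ET Visit (Day 175, Day 259, or 90 days after the last Part 2 dose) and a telephone contact one day later. Section 7.5 says that after an LP in the Follow-up Period participants stay about 1 hour in clinic and "will receive a safety follow-up TC approximately 24 hours after the procedure".
- **Concomitant therapy and procedures.** Sections 7.7.1 and 7.7.2 define both only up to the Final/ET Visit.
- **Stated risk and analysis.** Section 3.3 lists LP complications and notes that "life-threatening cerebral herniation is a possible complication of a lumbar puncture procedure". Section 5.7.1 of the Part 1 SAP plans a table of "TEAEs related to the lumbar puncture by primary SOC and MedDRA preferred term", and Section 5.7.1 of the Part 2/integrated SAP plans the same one.

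**The concern.** The protocol plans a safety call to check on the last LP, but its written recording window has already closed when the call is made. A headache that begins that evening and is mentioned on the call falls outside Section 12.3.1. A serious infection or bleed that starts after the visit, and is judged due to the LP but not to the drug, falls outside the only reporting rule that Section 12.3.2 gives for that period. Treatment given for either event falls outside Sections 7.7.1 and 7.7.2.

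At stake are the completeness of LP safety data at one LP per participant, consistency between sites that may read the text differently, and the reporting of a serious procedural complication.

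**Working it through.** **1. Is the call after the final visit really part of the plan?** Sections 5.2.1 and 5.2.2 state the number of telephone contacts. Counting the contact columns in the schedules:

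| Schedule | Contacts counted | Total | Stated | Without the last contact |
|---|---|---|---|---|
| Table 1 (A, B, C1, C2) | Days 16, 30, 50, 58, 78, 86, 93, 131, 176 | 9 | 9 | 8 |
| Table 2 (D1, D2) | Days 16, 30, 50, 58, 78, 86, 106, 114, 134, 142, 162, 170, 177, 215, 260 | 15 | 15 | 14 |
| Table 3 (Part 2) | 3 loading + 38 maintenance + 2 follow-up | 43 | 43 | 42 |

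The stated totals reproduce only if the contact after the Final/ET Visit is included. Footnote 4 of Table 2 and footnote 3 of Table 3 make next-day contacts necessary only when an LP was done, which ties them to the LP.

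**2. Which events does the text cover?**

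| Onset and type | Position under the written rules |
|---|---|
| At the visit or in the 1-hour observation | Inside the window; followed if ongoing (12.3.1, 12.3.2) |
| After the visit, non-serious, heard on the call | Outside 12.3.1; nothing says it is recorded |
| After the visit, serious, drug-related | Reportable (12.3.2) |
| After the visit, serious, LP-related only | Not reportable under the 12.3.2 rule; 12.3.3 points the other way |
| After the call, non-serious | Not collected |

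**3. What share of LPs is affected?** Days with CSF sampling:

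- Cohorts A to C2, Part 1: Days 1, 15, 29, 57, 85, 92, 130, 175 = 8. Share 1/8 = 12.5%.
- D1/D2 not entering Part 2: Days 1, 15, 29, 57, 85, 113, 141, 169, 176, 214, 259 = 11. Share 1/11 = 9.1%.
- D1/D2 completing the longest Part 2 schedule: 8 in Part 1 (the Day 176 LP is omitted under footnote 30, and Days 214 and 259 are skipped) + 41 dosing visits + 2 follow-up visits = 51. Share 1/51 = 2.0%.

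D1 and D2 make up 48 + 18 = 66 of the 98 planned participants, so the smallest share may apply to many of them.

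**4. Direction.** The treatment-emergent definition in both SAPs has a start but no end date. An event from the last call is therefore analysed if the site recorded it and lost if it did not. The error can only lower the count. The documents give no LP complication rate by time since puncture, so its size cannot be calculated.

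**The case against.** The best defence is that other text keeps recording open. Section 5.2.2 lets a participant's end of study be the last follow-up contact or the date an AE resolves. Section 12.3.3 requires SAE reports regardless of relationship to study treatment, and 12.3.3.1 requires all causes of death to be reported as SAEs. Section 12.6.1 tells the investigator to record all AEs. Table 3 marks AE recording as ongoing, and Table 2 carries one spanning entry. A careful site would probably record what it heard on the call.

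This shows that the passages conflict; it does not settle which governs. None of them states an end to the window, whereas 12.3.1 and 12.3.2 do, and 12.3.3 does not say whether it overrides the specific rule for later SAEs. How far the AE row runs in Table 1 cannot be confirmed from the extracted table.

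The defence does defeat three stronger readings that a reader might infer:

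- *All complications of every last LP go uncollected.* Events starting at the visit or in the observation hour are captured and followed, and a safety call is planned.
- *The primary endpoint is materially biased.* That endpoint is overall AE and SAE incidence. Participants are counted once per system organ class or preferred term in the severity and relationship summaries, so losing one LP need not change incidence in proportion. The last LP is a non-dosing one on the same schedule in both Part 1 arms, so nothing points to a between-arm difference.
- *A further 32 Day 175 LPs (8 + 8 + 12 + 4 in Cohorts A to C2) are lost when those participants enter Part 2.* This assumes that the window closes between the parts. Section 12.3 can equally be read as one window ending at the Part 2 visit.

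**Conclusion.** The point holds as a conflict in the protocol's wording with a limited safety consequence. AEs that start after the Final/ET Visit are outside the written window, including those heard on the planned call. An LP-related, not drug-related SAE that starts then has no clear reporting duty.

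The gap concerns one LP per participant, with the shares above. Those shares assume that every scheduled LP is done; the 1 in 51 also assumes the maximum Part 2 duration, which the early termination described in the Part 2/integrated SAP makes less likely. LP-related events can only be under-counted, by an unknown amount. The documents do not support a claim of total loss of follow-up after the last LP, of a meaningful shift in the primary endpoint, or of bias between arms.

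**What to change.** - In Sections 12.3.1, 12.3.2, 7.7.1 and 7.7.2, end collection at the telephone contact already scheduled after the Final/ET Visit, or at the visit itself if no contact is required.
- In Section 12.3.2, extend the rule for later SAEs to events considered related to study treatment or to the LP procedure, matching the two judgements in 12.2.2.
- State which Final/ET Visit closes the window for participants who enter Part 2.

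The change is to wording only: the call and the LP causality judgement already exist. The cost is a few more AE records. It does not close the gap fully, because delayed non-serious events that start after the call remain uncollected. As the study has been terminated early, the study report should at least say how events after the final LP were handled.
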